# Clinical Study Protocol

## Johnson & Johnson Vision Care, Inc.

Visit 1: Treatment 1 Lens Fitting			
Step	Procedure	Details	
		
visit. No additional lenses will be dispensed.
 
 
• A new lens will be opened and worn each day.
 
• Instruct the subject to bring back all unworn study lenses.
 
• Instruct the subject no cleaning or disinfecting solutions will be used for this lens type.
 
• If determined necessary by the Investigator sterile non-preserved rewetting drops may be dispensed to be used as needed for dryness.
 
• Subjects will be instructed to wear lenses for a minimum of 6 hours a day, every day during the study.
 
• Subjects will be instructed to wear their glasses when not wearing the study lenses.
 
• A patient instruction booklet will be provided.
 
 
NOTE: In the event a lens is lost or damaged, the subject will return to the clinical site for replacement. As much as reasonably possible, a damaged lens and packaging should be returned to the clinical site (wet, if possible) and then returned to the Sponsor. If lens damage is present, complete the Product Quality Complaint Form. The lens will be stored in labeled vial with saline, and clearly differentiated from the other worn lenses that will be shipped back to the Sponsor.
	
1.31	Schedule Follow-up	
The subject will be scheduled to return for their follow-up appointment in 3±1 days.
 
NOTE: To count the follow-up visit as a day of wear the Subject must have worn the study lenses for 6 hours prior to the visit.
	

# Clinical Study Protocol

## Johnson & Johnson Vision Care, Inc.

### VISIT 2

The subjects must present to Visit 2 wearing the study lenses. To be counted as a day of wear the lenses need to have been worn for at least six (6) hours prior to the visit.

Visit 2: Treatment 1 Follow-up 1			
Step	Procedure	Details	
2.1	Adverse Events and Concomitant Medications Review	Review the subject's concomitant medications and record any changes from the previous study visit. Record any adverse events or medical history changes from the previous study visit.	
2.2	Wear time and Comfortable Wear time with Study lenses	Record the hours the subject has worn the study lenses and the comfortable wear time on the day of follow-up.	
2.3	Compliance	Record the subject's compliance with wearing the study lenses.  NOTE: Subjects must have worn lenses for at least 6 hours per day. To be counted as a day of wear at this visit the Subject must have worn the study lenses for 6 hours prior to the visit.	
2.4	Ocular Symptoms	Subjects will respond to a verbal open-ended symptoms questionnaire.	
2.5	Subjective Acceptance	Record whether the subject's distance and near vision with the lenses is acceptable.	
2.6	Distance and Near Entrance Visual Acuity	Measure the distance and near visual acuity OD, OS and OU. Record the results.  Use the ETDRS 2000 Series Chart 1 or 2 near card placed at 40 cm to measure the Near visual acuity	
2.7	Distance Over-Refracton and Distance Visual Acuity	Perform a distance over-refraction OD and OS using loose lenses outside of the phoropter under ambient room illumination. The distance over-refraction may also be refined under binocular conditions. Record the results and distance visual acuity OD and OS.  The results of the distance over-refraction may also be checked for the impact on near vision under monocular and/or binocular conditions.	

**Clinical Study Protocol**  
**Johnson & Johnson Vision Care, Inc.**

Visit 2: Treatment 1 Follow-up 1			
Step	Procedure	Details	[REDACTED]
2.8	Determination of Lens Optimization	
If the subject reports unsatisfactory vision or is unable to obtain 20/30 distance visual acuity OU with the lenses, then a modification must be attempted.
 
If the subject reports satisfactory vision with the lenses a modification is not required, however at the Investigator's discretion and based upon their findings on the measured visual acuity and/or over-refraction the investigator may make a modification.
 
Up to two attempts at modification are permitted if necessary, in order to achieve an acceptable distance and near binocular performance for the subject, and to enable them to wear that particular lens type.
 
Follow the fitting guide and steps 1.22-1.27 in Visit 1 Fitting allowing for at least 10 minutes of settling time between each lens modification.
	Appendix F (Fitting Guide)
2.9	Lens Fit Assessment	
Evaluate and grade lens centration, primary gaze movement, upgaze movement and tightness (push-up test).
 
 
• The subject should not proceed to wear the lenses if any of the following is observed:
 
• presence of limbal exposure (appearance of clear cornea) in any gaze
 
• presence of edge lift
 
• presence of unacceptable movement (excessive or insufficient) in all three movement categories (primary gaze, upgaze, and push-up).
 
 
NOTE: If lens fit is unacceptable subject will be discontinued from the study. Remove the lenses, and complete the Final Evaluation forms.
	[REDACTED]
2.10	Collection of unworn lenses (if applicable)	
Collect unworn lenses returned by the subject when lens power has been optimized.
 
If lens power was not changed allow the subject to use the unworn lenses dispensed at
	

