### Unacceptable Lens Fit

Unacceptable lens fit will be assessed at all study visits (scheduled and unscheduled) for each subject eye. Unacceptable fit is a binary response where Y=1 if lens fit is unacceptable and Y=0 otherwise. Unacceptable fit was defined as unacceptable if any one of the following criteria:

- limbal exposure at primary gaze or with extreme eye movement;
- edge lift;
- excessive movement in primary up gaze;
- insufficient movement in all three of the following conditions: primary gaze, up gaze, and push up test.

Eyes with multiple unacceptable fitting events was counted only once. See [REDACTED] in Appendix H for additional details regarding lens fit assessments.

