#### **The Model:**

Let  $Y_1$  and  $Y_2$  denote the binary outcomes of lens fit acceptance (Yes/No) in left and right eyes, respectively, across dispensing and follow-up visits when wearing the Test lens. Considering the correlation,  $\rho$ , between  $Y_1$  and  $Y_2$ , the distribution of the sum  $Y = Y_1 + Y_2$  is obtained by the mixture of two variables. One of them follow a binomial distribution  $Bin(2, p)$  with mixing probability  $(1 - \rho)$  and the other one follows a modified Bernoulli distribution,  $MBern(p)$ , taking value 0 and 2 rather than conventional 0 and 1, with mixing probability  $\rho$ :

$$P(Y = y | p, \rho) = (1 - \rho)Bin(2, p)I_{A1} + \rho MBern(p)I_{A2},$$

where  $I_{A1} = \{0, 1, 2\}$ ,  $I_{A2} = \{0, 2\}$  and  $p$  is the probability of success (i.e., acceptable lens fitting).

To overcome the complexity of the mixture likelihood a latent variable  $Z_i, i = 1, 2$  is introduced in the model to indicate in which component of the model the observation  $y_i, i=1, 2$ , belongs to, that is,

$$Z_i = \begin{cases} 1, & \text{if the observation belong to the MBern}(p), \\ 0, & \text{if the observation belong to the Bin}(2, p) \end{cases}$$

The joint distribution of the augmented data  $(Y_i, Z_i), i = 1, 2$ , is given by

$$\begin{aligned} P(Y = y_i, Z = z_i | p, \rho) \\ = \rho^{z_i} p^{y_i z_i / 2} (1 - p)^{(2 - y_i) z_i / 2} (1 - \rho)^{1 - z_i} \binom{2}{y_i} p^{y_i (1 - z_i)} (1 - p)^{(2 - y_i) (1 - z_i)} \end{aligned}$$

The probability  $p$  links to the regression variables through a logit transformation as follow:

$$\text{logit}(p) = \beta_0 + \beta_1 \text{lens}$$

It is assumed that  $\beta_0, \beta_1$  and  $\rho$  to be independent with a non-informative prior  $N(0, 1000)$  for  $\beta_0$  and  $\beta_1$ , and  $\text{beta}(0.5, 0.5)$  for  $\rho$ . The Metropolis sampler algorithm as implemented in the SAS/STAT MCMC Procedure will be used to estimate the posterior distributions of the

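### For subjects whose lenses are changed at Visit 2, the step order gives no after-wear fit grade for the lenses worn since Visit 1, so one assessment of a gating co-primary endpoint is lost

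*Combined protocol and SAP*

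**What the plan says.** Section 2.2 defines the fit endpoint by visit and by eye: "Unacceptable lens fit will be assessed at all study visits (scheduled and unscheduled) for each subject eye". It is an any-failure endpoint: "Eyes with multiple unacceptable fitting events was counted only once". The model statement in Section 14.5 takes outcomes "across dispensing and follow-up visits when wearing the Test lens". The hypothesis is that the eye-level rate is below 5%. Both safety hypotheses must be met before any efficacy hypothesis is tested (Sections 2.3 and 14.4).

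For Visit 2, Section 7.2 says "The subjects must present to Visit 2 wearing the study lenses". The steps are then:

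- **2.1 to 2.7:** adverse events, wear time, compliance, symptoms, acceptance, acuity and over-refraction. None grades fit.
- **2.8:** if vision is unsatisfactory or 20/30 is not reached, "then a modification must be attempted". If vision is satisfactory, "based upon their findings on the measured visual acuity and/or over-refraction the investigator may make a modification". For a changed lens the instruction is "Follow the fitting guide and steps 1.22-1.27 in Visit 1 Fitting allowing for at least 10 minutes of settling time between each lens modification". Step 1.27, within that range, is the fit assessment.
- **2.9:** fit is graded, with a note that an unacceptable fit leads to discontinuation.
- **2.11 and 2.13:** the lenses are removed, and the new pair dispensed must match the powers of the removed pair.

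Table 3 marks fit assessment at all three visits. At Visit 2 it does not say which pair is graded.

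**The concern.** Misfit that appears only after wear can be seen only at a follow-up visit. There are two scheduled ones, Visits 2 and 3. If a subject's lenses are changed at step 2.8, the pair on the eye at step 2.9 is the new one, settled for about 10 minutes and already graded at step 1.27. The pair the subject arrived in comes off ungraded. That subject keeps one after-wear assessment, at Visit 3 and on a different power or ADD. A subject modified and then discontinued at Visit 2 for vision or comfort has none, yet still belongs to the safety population in which the endpoint is analysed.

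Because any failure counts, leaving out an assessment cannot raise the observed rate. The error can run only towards passing the first gate of the testing sequence.

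**Working it through.** **1. The plan's own figure.** The only number tied to this endpoint is the 92.6% power at 100 subjects in Table 8. With the stated inputs (2% rate, between-eye correlation 0.70) and the Section 14.5 model, I obtain about 54.5%. Section 14.2 does not give the priors or zero-event handling of the sponsor's simulation, so I treat this as a separate question. Nothing below depends on it.

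**2. Which pair is graded, and when**

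| Subject | Fit grades of the power/ADD worn from Visit 1 to Visit 2 | Fit grades of the modified pair |
|---|---|---|
| Not modified at Visit 2 | 1.27, 2.9, 3.10 | none |
| Modified, completes | 1.27 only | 1.27 as repeated under 2.8, 2.9, 3.10 |
| Modified, leaves at 2.15 for vision or comfort | 1.27 only | 1.27 as repeated, 2.9 |
| Modified, fails fit at 2.9 | 1.27 only | 2.9 failure, already an event |

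Step 1.29 dispenses only if fit is acceptable. For every dispensed subject the Visit 1 grade of that pair is therefore acceptable by construction and cannot show a later misfit.

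**3. Number of missing grades.** The modification rate is not stated. Assuming 20% to 50% of 100 subjects (200 eyes): 0.20 × 200 = 40 and 0.50 × 200 = 100 eyes without an after-wear grade at Visit 2. These are missing grades, not missed failures.

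**4. Effect of one unrecorded failure.** I used the Section 14.5 likelihood, with p the probability of an unacceptable fit and Y the number of failing eyes:

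- P(Y=0) = (1−ρ)(1−p)² + ρ(1−p)
- P(Y=1) = 2(1−ρ)p(1−p)
- P(Y=2) = (1−ρ)p² + ρp

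The priors were logit(p) ~ N(0, 1000), with 1000 read as a variance, and ρ ~ Beta(0.5, 0.5). The lens coefficient was dropped because there is one lens. The criterion is that the 97.5th posterior percentile of p lies below 5%. Results by numerical grid:

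| Subjects | 1 bilateral event | 2 | 3 |
|---|---|---|---|
| 100 | 3.2% pass | 5.08% fail | 6.7% fail |
| 102 | 3.1% pass | 4.98% pass | 6.6% fail |
| 114 | 2.8% pass | 4.5% pass | 5.9% fail |
| 120 | 2.7% pass | 4.2% pass | 5.6% fail |

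The relevant row depends on the denominator. Section 14.5 uses the safety population, not completers. In Table 6 the historical safety populations sum to 33+44+78+68+75+78+37 = 413, out of 34+48+81+71+78+81+40 = 433 enrolled. That is 95.4%, and 0.954 × 120 ≈ 114. At that size the third bilateral event decides, not the second.

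**5. Effect on the chance of wrongly passing (illustration).** Take a true eye rate of 5%, ρ = 0.7 and 100 subjects. If a share m of events goes unrecorded, the recorded rate is 5% × (1−m).

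| m | 0 | 5% | 10% | 20% | 30% |
|---|---|---|---|---|---|
| Chance of passing | 6.4% | 7.9% | 9.8% | 14.6% | 21.2% |

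The documents give no value for m.

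**The case against.** The best reply is that little is lost. The power and ADD worn to Visit 2 were graded at Visit 1, and that grade enters the endpoint. Table 1 lists one base curve (8.35 mm) and one diameter (14.3 mm). A misfit caused by either should recur in the modified pair, which is graded at Visit 2 and again at Visit 3 after about a week. Table 7 gives a historical rate of 0%. This stands as an argument about size. It does not supply the missing grade, and center thickness varies with power, so two powers need not fit identically.

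The fitting guide (Appendix F) and the lens-fitting procedure (Appendix H) are redacted and may say when the arriving pair is graded. Table 3 lists fit assessment above modifications, which is compatible with grading first. Both are fair cautions, but the readable numbered steps say otherwise.

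A reader might also infer three stronger things that the documents do not support:

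- **That the fit of these lenses is never recorded, after three days on the eye.** Step 1.27 records it for that power and ADD, and a new lens is opened each day. Only the after-wear grade is missing.
- **That the loss is concentrated in poorly fitting eyes because poor fit causes poor vision.** No section makes that link, and poor centration is not itself an endpoint criterion in Section 2.2. The downward direction does not need it.
- **That subjects who fail step 2.9 are lost events.** They are already counted as failures.

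**Conclusion.** The point holds for subjects whose lenses are changed at Visit 2. The written order yields no after-wear fit grade for the lenses they arrived in, although the endpoint is assessed at every visit and any failure counts. The direction is certain: the gap can only favour meeting the below-5% criterion. The size cannot be determined, because neither the modification rate nor the share of misfits visible only after wear is given. The fixed geometry, the later grades and the 0% historical rate suggest it is small.

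It would be tempting to conclude that one missed subject flips the result. That is so only exactly at the boundary: two bilateral events at 100 subjects, or three at about 102 to 120. These boundaries rest on the Section 14.5 priors as read above and on bilateral events. The case for acting is that the endpoint opens all efficacy testing and the repair is cheap, not that a large bias has been shown.

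**What to change.** At Visit 2, grade and record the fit of the arriving pair before any step 2.8 lens change. Keep step 1.27, already required by step 2.8, as the grade for each modified pair. Label the two in the eCRF as arriving pair and modified pair, and state in Sections 2.2 and 14.5 that an unacceptable grade on either counts for the endpoint.

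Moving step 2.9 unchanged would carry its discontinuation note onto the arriving pair before any modification had been tried. The sponsor should therefore reconcile that note with steps 2.8 and 2.9, Section 2.2 and Table 3. No clinical rule is proposed here.

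The cost is an eCRF label and one grading. The grading is moved, if step 1.27 replaces step 2.9 for modified pairs, or added, if step 2.9 is kept as well. Unmodified subjects need no extra grading. The observed fit-failure rate may come out slightly higher.

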**Clinical Study Protocol**  
**Johnson & Johnson Vision Care, Inc.**

Visit 2: Treatment 1 Follow-up 1			
Step	Procedure	Details	[REDACTED]
		Visit 1 and dispense enough lenses of the same power to last the subject until their next visit.	
2.11	Lens Removal	The study lenses will be removed and discarded.	
2.12	Biomicroscopy	Perform biomicroscopy OD and OS. Slit Lamp Classification Scales will be used to grade the findings.  If the clearance of the fluorescein needs to be expedited, preservative-free rewetting drops may be instilled.	[REDACTED]
2.13	Insertion of Study Lenses	Dispense the subject a new pair of lenses that match the distance and ADD power of the lenses that were removed in Step 2.11 above.	
2.14	Distance and Near Exit Visual Acuity	Distance and near Snellen visual acuity will be measured for each eye with the study contact lenses in place. For near measures use the ETDRS 2000 Series Chart 1 or 2. The acuity will be recorded to the nearest letter OD, OS and OU.  NOTE: The distance visual acuity must be at least 20/30 OU for the lenses to be dispensed.	[REDACTED]
2.15	Dispensing Criteria	The following criteria must be met for lenses to be dispensed and if all are not met the subject will be discontinued. 
 
• Distance Snellen acuity equal to or better than 20/30 OU
 
• Subject must indicate that the vision is acceptable.
 
• Subject must indicate that the comfort of the lenses is acceptable.
 
• Lenses must have an acceptable general lens fit.
 
	
2.16	Patient Instructions	Instruct the Subject the following: 
 
• The lenses will be worn on a daily wear basis.
 
	

# Clinical Study Protocol

## Johnson & Johnson Vision Care, Inc.

Visit 2: Treatment 1 Follow-up 1			
Step	Procedure	Details	
		
 
• Only enough lenses will be dispensed to the subject to wear for the required number of days until their follow-up visit. No additional lenses will be dispensed.
 
• A new lens will be opened and worn each day.
 
• Instruct the subject to bring back all unworn study lenses.
 
• Instruct the subject no cleaning or disinfecting solutions will be used for this lens type.
 
• If determined necessary by the Investigator sterile non-preserved rewetting drops may be dispensed to be used as needed for dryness.
 
• Subjects will be instructed to wear lenses for a minimum of 6 hours a day, every day during the study.
 
• Subjects will be instructed to wear their glasses when not wearing the study lenses.
 
• Remind the subject to bring their habitual correction to the follow-up visit.
 
 
NOTE: In the event a lens is lost or damaged, the subject will return to the clinical site for replacement. As much as reasonably possible, a damaged lens and packaging should be returned to the clinical site (wet, if possible) and then returned to the Sponsor. If lens damage is present, complete the Product Quality Complaint Form. The lens will be stored in labeled vial with saline, and clearly differentiated from the other worn lenses that will be shipped back to the Sponsor.
	
2.17	Schedule Follow-up	The subject will be scheduled to return for their follow-up appointment in 7±1 days.	

## Clinical Study Protocol

### Johnson & Johnson Vision Care, Inc.

Visit 2: Treatment 1 Follow-up 1			
Step	Procedure	Details	
		NOTE: To count the follow-up visit as a day of wear the Subject must have worn the study lenses for 6 hours prior to the visit.	

### VISIT 3

The subjects must present to Visit 3 wearing the study lenses. To be counted as a day of wear the lenses need to have been worn for at least six (6) hours prior to the visit.

Visit 3: Treatment 1 Follow-up 2			
Step	Procedure	Details	
3.1	Adverse Events and Concomitant Medications Review	Review the subject's concomitant medications and record any changes from the previous study visit. Record any adverse events or medical history changes from the previous study visit.	
3.2	Wear time and Comfortable Wear time with Study lenses	Record the hours the subject has worn the study lenses and the comfortable wear time on the day of follow-up.	
3.3	Compliance	Record the subject's compliance with wearing the study lenses.  NOTE: Subjects must have worn lenses for at least 6 hours per day To be counted as a day of wear at this visit the Subject must have worn the study lenses for 6 hours prior to the visit.	
3.4	PRO (CLUE and MRD) and CLDEQ-8 Questionnaires	The subject will evaluate the vision characteristics, comfort characteristics, handling characteristics, and visual symptoms of the study lenses using the PRO (CLUE and MRD) & CLDEQ-8 questionnaires.	Appendix A [REDACTED]
3.5	Ocular Symptoms	Subjects will respond to a verbal open-ended symptoms questionnaire	[REDACTED]
3.6	Subjective Acceptance	Record whether the subject's distance and near vision with the lenses is acceptable.	
3.7	Distance and Near Entrance Visual Acuity	Distance and near Snellen visual acuity will be measured for each eye with the study contact lenses in place.	[REDACTED]

**Clinical Study Protocol**  
**Johnson & Johnson Vision Care, Inc.**

Visit 3: Treatment 1 Follow-up 2			
Step	Procedure	Details	[REDACTED]
		For near measures use the ETDRS 2000 Series Chart 1 or 2. The acuity will be recorded to the nearest letter OD, OS and OU.	
3.8	Visual Performance Distance (4M) Intermediate (64 cm) Near (40 cm)	
Binocular Visual performance will be recorded for the following:
 
Distance, Bright Illuminance  High and Low Contrast ETDRS Charts            4M- HC#3 and LC#3
 
Near, Bright Illuminance  Reduced Guillon-Poling Charts Intermediate (64 cm) High Contrast and Low Contrast            Near (40 cm) High Contrast and Low Contrast
 
Distance, Dim Illuminance (with Distance goggles)  High Contrast ETDRS Charts 4M- HC#6
 
Near, Dim Illuminance (with Near goggles)  Reduced Guillon-Poling charts            High Contrast Intermediate (64 cm) and Near (40 cm).
 
Note:
 
 
• The room illuminance must be between 7.3 and 7.9 EV (394-597 lux).
 
• Distance, HC-1 Chart luminance Acceptable Range 10.5-10.7 EV (181-208 cd/m^2).
 
• Guillon-Poling, Near Chart Luminance Acceptable Range 10.8-11.1 EV (223-274 cd/m^2).
 
• Do not use the Mesopic filter for Dim luminance (Dim luminance will be simulated by using the goggles)
 
	[REDACTED]
3.9	Binocular Distance Over-refraction and Distance Visual Acuity	
Perform a binocular over-refraction and record the OD and OS results and distance visual acuity.
 
Note: No lens changes are allowed based on the over-refraction.
	Appendix G

**Clinical Study Protocol**  
**Johnson & Johnson Vision Care, Inc.**

Visit 3: Treatment 1 Follow-up 2			
Step	Procedure	Details	[REDACTED]
3.10	Lens Fit Assessment	
Evaluate and grade lens centration, primary gaze movement, upgaze movement and tightness (push-up test).
 
The subject should not proceed to wear the lenses if any of the following is observed:
 
 
• presence of limbal exposure (appearance of clear cornea) in any gaze
 
• presence of edge lift
 
• presence of unacceptable movement (excessive or insufficient) in all three movement categories (primary gaze, upgaze, and push-up).
 
 
NOTE: If lens fit is unacceptable subject will be discontinued from the study. Remove the lenses, and complete the Final Evaluation forms.
	[REDACTED]
3.11	Collection of unworn lenses (if applicable)	Collect unworn lenses returned by the subject.	
3.12	Lens Removal	
Have the subject remove the study lenses and store in saline in a labeled glass vial.
 
NOTE: Lenses do not need to be stored in a refrigerator.
	
3.13	Biomicroscopy	
Perform biomicroscopy OD and OS. Slit Lamp Classification Scales will be used to grade the findings.
 
If the clearance of the fluorescein needs to be expedited, preservative-free rewetting drops may be instilled.
	[REDACTED]

